7.1 Sample size

Previous results of Rodiera et al. yielded a bias (D) of -0.02 and limits of agreement (L) of -0.035 to -0.012 for the comparison of TOF cuff vs EMG at a TOF ratio of 0.7 and D 0.05 and L 0.04 – 0.06 at TOF 0.1.(6) We are not informed about D and L during deeper levels of neuromuscular block, and at TOF ratio 0.9 which is a clinically important level for safe extubation of a patient. Furthermore, precision was not assessed in this study and no comparisons were made with AMG and EMG.

We will therefore perform a pilot study with 200 patients (100 patients with normal BMI ($< 30 \text{ kg/m}^2$) and 100 patients with morbid obesity ($>30 \text{ kg/m}^2$)) to ensure that reliable estimates of repeatability coefficient (r), bias (D), and limits of agreement (L) are obtained. After 100 patients (50 non-obese/50 obese) we will perform an interim analysis and calculate the remaining number of patients needed to complete the study.

The protocol was amended (19-11-2018) to include 50 extra patients to investigate relative bias between ipsi- and contralateral comparisons between TOF Cuff and EMG in patients with normal BMI. The total number of included patients will be 250. A sub analysis of the first 20 patients shows that it takes 30 (SD 18.0) minutes until spontaneous recovery to a Tof Ratio of 0.9 is achieved. The EMG group required 47 minutes. To exclude possible outliers in our previous study we expect a mean time to a Ratio 0.9 of 42 minutes. With an α of 0.05 and β of 0.9 we require 24 patients. In the same sub analysis we saw that approximately half of the patients require additional muscle relaxants,

meaning that complete recovery is not achieved in half of the cases. In order to acquire a proper sample size to compare recovery to a Tof Ratio of 0.9 we will need a total of 50 patients to assess neuromuscular recovery on both ipsi- and contralateral extremities with the Tof Cuff.

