This is an observational, non-inferiority trial in which we will compare the TOF cuff device to electromyography (EMG). All patients will receive general total intravenous anesthesia (propofol/remifentanil/rocuronium). Patients will have the TOF cuff and EMG placed on the same extremity (hand for EMG, upper arm for TOF cuff). Measurements will be done during induction, maintenance and recovery from a moderate (GROUP 1) and deep (GROUP 2) neuromuscular block. Patients will enter the study in group 1 or 2 based on the required procedure. In other words, the procedure dictates the desired level of neuromuscular block (moderate or deep), not the study. We will perform a pilot study with 200 patients (150 patients with normal BMI ($< 30 \text{ kg/m}^2$) and 50 patients with morbid obesity ($> 35 \text{ kg/m}^2$) to ensure that reliable estimates of repeatability coefficient, bias, and limits of agreement are obtained. After 100 patients (50 non-obese/50 obese) we will perform an interim analysis and calculate the remaining number of patients needed to complete the study. The protocol was amended (19-11-2018) to include 50 extra patients to investigate relative bias between ipsi- and contralateral comparisons between TOF Cuff and EMG in patients. Total number of included patients will be 250. The interim analysis at 100 included patients showed a significant difference between the TOF Cuff and the EMG regarding the time to complete spontaneous recovery of neuromuscular block. The time to complete recovery is clinically the most relevant outcome as this reflects zero chance of residual NMB by definition. To increase the emphasis on time until full spontaneous recovery, the protocol was amended (19-6-19) to include 50 patients at the LUMC that were originally scheduled for inclusion at the Nederlandse Obesitas Kliniek (NOK). The very reason for this, is the fact that at the NOK, sugammadex reversal is routinely applied to facilitate quick changeover of patients. However, this practice interferes with the objective of

evaluating time until complete spontaneous (unreversed) recovery of the NMB. Transferal of 50 intended study subjects from the NOK to the LUMC will allow us to gather more data on the relevant final stages of the spontaneous recovery of NMB

1. Introduction

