We have successfully used the TOF cuff in the BLISS 2 and Neuropa studies.(7, 8) We find it to be far superior in ease of use over AMG. However, several reviewers questioned the validity of the device during the review process of both studies. A small validation study the TOF cuff has been conducted several years ago and produced acceptable bias and limits of agreement when compared to mechanomyography during recovery of a moderate neuromuscular block. However, the TOF cuff was

not assessed during deep neuromuscular block and not compared to EMG and the authors concluded that additional validation of the device is necessary.(6)

In this study we intend to further validate the TOF cuff and compare it to EMG during recovery of both moderate and deep neuromuscular block. We will study patients of normal and high body mass index values.

2. Objectives

To compare the bias, limits of agreement and precision of the TOF cuff relative to EMG during recovery of moderate and deep neuromuscular block in patients with normal body mass index and morbidly obese patients.

Hypothesis

The TOF cuff behaves similarly to EMG in terms of bias, limits of agreement and precision when comparing the TOF cuff to EMG.

3. Study design

This is an observational, non-inferiority trial in which we will compare the TOF cuff device to electromyography (EMG). We will do this in 100 patients with $BMI < 30 \text{ kg/m}^2$ and 50 patients with $BMI > 35 \text{ kg/m}^2$. The protocol was amended (19-11-2018) to include 50 extra patients to investigate relative bias between ipsi- and contralateral comparisons between TOF Cuff and EMG in patients with normal BMI. Total number of included patients will be 250. The preliminary analysis after 100 patients showed that a significant difference occurs in the comparison between the TOF Cuff and the EMG regarding the time to full recovery of neuromuscular block. The time to complete recovery is clinically the most relevant outcome. To increase emphasis on time until full recovery, the protocol was amended (19-6-19) to include 50 patients in the LUMC which were originally scheduled for the NOK. In the NOK sugammadex is routinely administrated which disables evaluation of the time until complete recovery.

All patients will receive general total intravenous anesthesia (propofol/remifentanil/rocuronium). Patients will have the TOF cuff and EMG placed on one extremity (hand for EMG, upper arm for TOF cuff).

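### Section 7.1 states an obese stratum of 100 patients at BMI above 30, while the abstract and section 4.1 state 50 at BMI above 35; section 3's counts do not reach its own total

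*Combined protocol and SAP*

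**What the plan says.** The objective is to compare agreement and precision of the two devices in normal-BMI and morbidly obese patients, so the size and definition of the obese stratum are part of the design.

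- **Section 7.1** plans a "pilot study with 200 patients (100 patients with normal BMI" and "100 patients with morbid obesity", with the cut-offs printed as below 30 and above 30 kg/m².
- **Abstract, Methods** plans a "pilot study with 200 patients (150 patients with normal BMI" "and 50 patients with morbid obesity", with the cut-offs printed as below 30 and above 35 kg/m². **Section 4.1** gives the same counts and cut-offs.
- **Section 3** says "We will do this in 100 patients with" BMI below 30 and 50 with BMI above 35, adds 50 extra patients, and then says "Total number of included patients will be 250".
- **Section 11.1** assigns BMI below 30 to the LUMC and BMI above 30 to the NOK.
- **Section 7.1 and the abstract** place the interim identically: "After 100 patients (50 non-obese/50 obese) we will perform an interim analysis".
- **Section 3** (and, in similar words, the abstract and 4.1) records the amendment of 19-6-19 to "include 50 patients in the LUMC which were originally scheduled for the NOK". Section 7.1 does not mention this amendment.

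**The concern.** These are all current, operative sections, so the difference is not one between an amendment record and the text that replaced it. The sample-size section and the population section cannot both be right about how many obese patients are planned, or about who counts as obese.

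Two things are at stake. First, section 7.1 is where the numbers are justified, and it attaches its aim of dependable estimates of repeatability, bias and limits of agreement to an obese group twice as large as the one in 4.1. Second, the cut-off decides who is analysed in that group. If it stays open, the assignment of patients with BMI 30 to 35 could be settled after data have been seen, and the abstract reports that the interim has already taken place.

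**Working it through.** **1. The counts side by side.** All figures are from the protocol.

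| Place | BMI <30 | Obese | Obese cut-off | Sum | With 50 extra |
|---|---|---|---|---|---|
| 7.1 | 100 | 100 | >30 | 200 | 250 |
| Abstract | 150 | 50 | >35 | 200 | 250 |
| 4.1 | 150 | 50 | >35 | 200 | 250 |
| 3 | 100 | 50 | >35 | 150 | 200 (250 stated) |
| 11.1 | not given | not given | >30 | – | – |

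The figure in 7.1 reproduces: 100 + 100 = 200, and 200 + 50 = 250. The abstract and 4.1 also reach 250, from 150 + 50 + 50. Section 3 falls 50 short.

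**2. Size of the discrepancy.** 100 / 50 = 2.0. The obese share of the 200 is 50% under 7.1 and 25% under 4.1; of the 250 it is 40% and 20%.

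**3. Likely origin (an inference).** Moving 50 patients from the obese site to the normal-BMI site turns 100/100 into 150/50: 100 + 50 = 150 and 100 − 50 = 50. Section 11.4 fits the older split: 20 weeks × 5 patients per week = 100 per site. So 7.1 appears not to have been updated for the June 2019 transfer. The protocol does not state the BMI of the transferred patients, and the transfer does not explain the two cut-offs.

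**4. Interim.** After 50 non-obese and 50 obese patients, the planned obese patients still to come are 50 − 50 = 0 under 4.1 and 100 − 50 = 50 under 7.1.

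**5. Cut-off.** A patient with BMI between 30 and 35 belongs to the obese group under 7.1 and 11.1, and to neither group under the abstract, 3 and 4.1.

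**6. Precision in the obese stratum.** With between-patient variance B, within-patient variance W and m measurements per patient, the variance of the estimated bias is (B + W/m)/n. For equal m, the ratio of confidence-interval widths is sqrt(100/50) = 1.41, whatever B, W and m are.

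For illustration, take one difference per patient and express 95% half-widths in units of the SD of the differences:

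- Bias, 1.96/sqrt(n): 0.28 SD at n = 50, 0.20 SD at n = 100.
- Each limit of agreement, 1.96 × sqrt(1/n + 1.96²/(2(n − 1))): 0.48 SD at n = 50, 0.34 SD at n = 100.

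**7. Does any stated calculation use the split?** The only one in 7.1 concerns time to a TOF ratio of 0.9. With a difference of 42 − 30 = 12 minutes, SD 18, two-sided alpha 0.05, and the stated 0.9 read as power, the paired formula gives (1.96 + 1.28)² × (18/12)² = 10.5 × 2.25 = 23.6, rounded up to 24. This matches the protocol and contains no BMI count.

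**The case against.** The strongest case on the other side is that this is a stale sentence with little practical effect.

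- **The precision aim does not rest on 100 obese patients alone.** The abstract states the same aim, in almost the same words, for the 150/50 split. This stands. A reader might infer that the sample-size justification collapses when the obese group is halved; the protocol does not support that.
- **No number depends on the split.** The total is 250 either way, the 24-patient calculation is untouched, and section 7 sets no stratum-specific criterion. This stands. A reader might infer that the obese comparison is underpowered, but no power or precision target is stated for it to miss.
- **The BMI 30 to 35 gap is narrower than it looks.** Sections 4.2 and 4.3 set no BMI limit, which may suggest that such patients are simply eligible. But 4.1 already describes the included patients as below 30 or above 35. What remains is the conflicting cut-off in 7.1 and 11.1.
- **Recruitment is hardly affected.** If the interim had its stated composition, all 50 obese patients planned in 4.1 were enrolled by then. A reader might infer that another 50 are owed; under 4.1 they are not.
- **Absolute interval widths are uncertain.** The protocol gives no SD of the differences for this comparison in obese patients, so only the ratio of 1.41 is firm. This stands.

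None of this reconciles 100 at above 30 with 50 at above 35, or section 3's 200 with its 250.

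**Conclusion.** Wrong as written: an internal inconsistency rather than a questionable design choice, of low to moderate severity. A stated stratum size and the cut-off that defines the stratum are incorrect in at least one place, and section 3's counts miss its stated total by 50.

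The obese group in 7.1 is exactly twice that in the abstract and 4.1. The interval for bias in that group is about 1.41 times wider at 50 than at 100, assuming equal measurements per patient. The effect falls on how the obese stratum is described and analysed, more than on recruitment.

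That 7.1 missed the June 2019 update is an inference. The conclusion does not depend on it, because the conflict is there whatever its cause.

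**What to change.** - Restate 7.1 as 150 (BMI below 30) + 50 (BMI above 35) + 50 extra normal-BMI patients = 250, and correct section 3 to the same counts.
- Use one cut-off, above 35 as in the abstract, 3 and 4.1, in 7.1 and 11.1. It should govern further enrolment and define the obese stratum.
- Ask the sponsor to confirm which cut-off was applied to patients already enrolled. Section 11.1 directs the NOK to enrol above 30, so some may have BMI 30 to 35; the number is unknown.
- Keep any such patients in the overall analysis, and show the obese-stratum results with and without them as a sensitivity analysis. Dropping them outright would be an exclusion made after the interim results were known.

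The cost is wording in sections 3, 7.1 and 11.1, one check of enrolled BMI values and one sensitivity analysis. The downside is that the stated obese stratum becomes smaller and, if some enrolled patients have BMI 30 to 35, the number above 35 may be below 50.

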7.2 Handling and storage of data and documents

All patients will be addressed to a random patient identification code. Patient identifying data will be omitted. The codebook will be stored digitally and will be safeguarded by the investigator. The digital form will be encrypted. Other involved parties (monitor, DSMB, ethical reviewing committee, Inspectie, Gezondheidszorg en Jeugd) could be granted access to patient data, also patient identifying data, to review if the research is being executed safely. These involved parties will handle the patient identifying data in a confidential manner. The sponsor, local researchers and project leader are responsible for data processing. When a subject withdraws consent, data collected until that moment will be used. All data will be stored for the length of the study and for 15 years afterwards, for further publication. All handling of personal data will comply with the Dutch Personal Data Protection Act.

The Functionaris Gegevensbescherming from the LUMC has been informed about the data handling in the ToCuff-trial. When subjects have questions or complaints about data handling they can contact the Functionaris Gegevensbescherming (contact information is mentioned in the patient information letter).

Only data needed to assess primary- and secondary objectives will be collected (see paragraph 8).

8. SAFETY

8.1 Adverse Events

An adverse event (AE) is any untoward medical occurrence in a patient or clinical investigation subject administered a pharmaceutical product, including placebo, and which does not necessarily have to have a causal relationship with treatment. An AE can be:

- Any unfavourable and unintended sign (including an abnormal laboratory finding), symptom, or disease temporally associated with the use of study medication, whether or not considered related to the study medication.
- Any new disease or exacerbation of an existing disease.
- Any deterioration in protocol-required or non-protocol-required measurements of laboratory value or other clinical tests (e.g. ECG or X-ray) that results in symptoms, a change in treatment, or discontinuation from study medication.

- Recurrence of an intermittent medical condition (e.g. headache) not present at baseline.

Subjects with AEs that are ongoing at the subject's completion/discontinuation visit (last treatment visit) will be followed up for 7 days and the follow up information will be recorded in the CRF. New AEs that are reported in the 7 days following the subject's completion/discontinuation visit will be recorded in the AE section of the CRF. Any AE that is still ongoing 7 days after the completion/discontinuation visit will have an end date of 'ongoing' in the CRF, however the investigator will continue to follow up ongoing AEs and record information in the source documents. SAEs will be followed until the event resolves or the event or sequels stabilize and this information will be reported to the Sponsor using the SAE Data Form.

8.2 Reporting of Adverse Events

For subjects who receive study medication, all AEs (learned through spontaneous reports, subject interview) starting from providing informed consent for study participation through the period beyond study completion will be collected on the AE pages of the CRF. In addition, a note should be made in the source documentation of the subject.

For each AE on the AE pages of CRF, the following information will be recorded: AE (e.g. headache), start date, start time, stop time, severity, study medication action taken, other action taken, relationship to study medication, outcome, seriousness. A cluster of signs and symptoms that results from a single cause should be reported as a single AE (e.g. fever, elevated WBC, cough, abnormal chest x-ray, etc. can all be reported as "pneumonia.").

8.3 Criteria for Assessing Severity

The Investigator will evaluate the comments of the subject and the response to treatment in order that he/she may judge the true nature and severity of the AE. Severity refers to the accumulated intensity of discomfort/impairment of health since the last recording of AEs and will be assessed according to the following criteria:

Mild: Awareness of sign, symptom, or event, but easily tolerated.

Moderate: Discomfort enough to cause interference with usual activity and may warrant intervention.

Severe: Incapacitating with inability to do usual activities or significantly affects clinical status and warrants intervention.

The criteria for assessing severity are different to those used for seriousness (see below for the

definition of an SAE).

8.4 Criteria for Assessing Causality

The question of the relationship of an AE to study medication should be determined by the Investigator after thorough consideration of all facts that are available. Assessment of causality is based on considering associative connections (time or place), pharmacological explanations, previous knowledge of the drug, presence of characteristic clinical or pathological phenomena, exclusion of other causes, and/or absence of alternative explanations. The causal relationship of an AE to study medication will be assessed according to the following criteria (based on World Health Organisation definitions):

Not related: Temporal relationship to study medication administration is missing or implausible, or there is an evident other cause.

Related

Unlikely to be related: Temporal relationship to study medication administration makes a causal relationship improbable; and other drugs, chemicals, or underlying disease provide plausible explanations.

Possibly related: Reasonable time sequence to administration of study drug, but event could also be explained by concurrent disease or other drugs or chemicals. Information on drug withdrawal may be lacking or unclear.

Probably related: Reasonable time sequence to administration of study drug, but unlikely to be attributed to concurrent disease or other drugs or chemicals, and which follows a clinically reasonable response on withdrawal (dechallenge). Rechallenge information is not required.

Definitely related: Plausible time relationship to study medication administration; event cannot be explained by concurrent disease or other drugs or chemicals. The response to withdrawal of the drug (dechallenge) should be clinically plausible. The event must be definitive pharmacologically or phenomenologically, using a satisfactory rechallenge procedure if necessary.

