8.7 Expedited Reporting

Adverse Reaction. Any untoward and unintended responses to an investigational medicinal product related to any dose administered. All AEs judged by either the reporting Investigator or the Sponsor as having a reasonable causal relationship to a medicinal product qualify as adverse reactions. The expression "reasonable causal relationship" means to convey in

general that there is evidence or argument to suggest a causal relationship (i.e. causality is at least “unlikely”).

Unexpected Adverse Reaction. An adverse reaction, the nature or severity of which is not consistent with the applicable product information (e.g. Investigator' Brochure for an unregistered investigational product or summary of product characteristics for a registered product). When the outcome of the adverse reaction is not consistent with the applicable product information this adverse reaction should be considered as unexpected.

Suspected Unexpected Serious Adverse Reaction (SUSAR). A SUSAR is an adverse drug reaction, which is both serious and unexpected. If an SAE was assessed to be a SUSAR by the Sponsor, the Competent Authorities, ECs and Investigators must be informed as soon as possible but no later than 15 calendar days after the sponsor has first knowledge of the minimum criteria for expedited reporting. If the SUSAR was immediately life-threatening or fatal, it must be reported as soon as possible but no later than 7 calendar days after the sponsor has first knowledge of the minimum criteria for expedited reporting. Relevant follow-up information should be communicated to the competent authority and the Ethics Committee within an additional 8 calendar days. The Sponsor is responsible for expedited reporting of SUSARs and other reportable events and safety issues to the Competent Authorities, according to local legislations. Investigators will be informed by the Sponsor. The Investigator or Sponsor, depending on local regulations, must inform the EC/IRB about SUSARs and other reportable events and safety issues in accordance with ICH guidelines and the practices of the governing ECs.

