9. ETHICS

Ethics Committees. The protocol, possible protocol amendments, the patient information form, informed consent form and any other study related information or documents will be reviewed and approved by the LUMC ethics committee (METC) before subjects are screened for study entry. The Investigator will submit periodic reports and inform the METC of any reportable adverse events (AEs) per ICH guidelines and local EC standards of practice.

Ethical Conduct of the Study. This study will be conducted in accordance with LUMC standard operating practices, which are designed to ensure adherence to Good Clinical Practice (GCP) guidelines as required by the following:

- Declaration of Helsinki, 1964 (“Recommendations Guiding Physicians in Biomedical Research Involving Human Patients”), and all its accepted amendments to date concerning medical research in humans.
- ICH Guideline for GCP (CPMP/ICH/135/95) of the European Agency for the Evaluation of Medicinal Products, Committee for Proprietary Medicinal Products, International Conference on Harmonization of Pharmaceuticals for Human Use. (Note for Guidance on Good Clinical Practice, 2002).
- European Union (EU) Clinical Trials Directive 2001/20/EC on the regulation of clinical trials in the EU and the implementation of GCP.
- GCP Directive 2005/28/EC.

This study will be conducted in accordance with national and local laws.

Subject Information and Consent. All subjects will be provided with oral and written information describing the nature and duration of the study and the procedures to be performed. Each subject will be given a copy of the informed consent and written information. The subject will be asked to sign an informed consent form prior to any study specific procedures being performed.

Benefits and risks assessment.

Patients will not have any benefit nor have a higher risk for adverse events when participating in this study. All devices used are noninvasive and pose no harm for the patient. We therefore content that there is no additional risk or burden for the patient.

Investigators and study personnel. Qualified Investigators under the sponsorship of the Leiden University Medical Center will conduct this study. The names of the investigators, independent physician and contact person are given on page 1 of this protocol. The Principle Investigator is GCP/GRP certified by the LUMC Boerhaave Committee.

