11.4 End of study report

Estimated study duration is 20 weeks (planned inclusion 5 patients/week in the LUMC and 5 in the Nederlandse Obesitas kliniek)

The investigator will notify the accredited METC of the end of the study within a period of 8 weeks. The end of the study is defined as the last patient's surgery.

In case the study is ended prematurely, the investigator will notify the accredited METC within 15 days, including the reasons for the premature termination.

Within one year after the end of the study, the investigator/sponsor will submit a final study report with the results of the study, including any publications/abstracts of the study, to the accredited METC.

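### Section 8 grades causality only against an undefined study medication, so an evident TOF cuff injury cannot be attributed to the device, while events judged improbable count as adverse reactions

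*Combined protocol and SAP*

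**What the plan says.** The Abstract describes the study in these words: "This is an observational, non-inferiority trial in which we will compare the TOF cuff device to electromyography (EMG". Section 3 repeats this. The object under test is a device. Rocuronium, propofol and remifentanil are the anesthetic that every patient receives.

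The safety section is framed around a drug:

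- Section 8.1 defines an adverse event (AE) for a person given a pharmaceutical product.
- Section 8.2 lists the CRF items for each AE. The one causality item concerns study medication.
- Section 8.4 opens with "The question of the relationship of an AE to study medication should be determined by the Investigator". Its lowest grade reads "Not related: Temporal relationship to study medication administration is missing or implausible, or there is an evident other cause". Four further grades (unlikely, possibly, probably, definitely) stand under the label Related, and all of them refer to the study medication or study drug.
- Section 8.6 includes the study medication, but no device, in the minimum content of the SAE form.
- Section 8.7 defines adverse reactions for medicinal products. It explains a reasonable causal relationship as "evidence or argument to suggest a causal relationship (i.e. causality is at least" the grade of unlikely.

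On device risk, Section 9 states: "All devices used are noninvasive and pose no harm for the patient".

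On timing, 8.1 says that subjects with AEs ongoing at a completion or discontinuation visit "will be followed up for 7 days and the follow up information will be recorded in the CRF". New AEs (8.1) and SAEs (8.5) are recorded over the same 7 days. Section 8.2 has collection continue past study completion, without an end date. Section 11.4 says "The end of the study is defined as the last" patient's surgery.

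**The concern.** A causality assessment should ask about the thing being studied. Here it asks about something the plan does not define, and it has no answer that points to the cuff or to EMG stimulation. The cuff is pressurised and stimulates repeatedly at supramaximal current (maximal plus 20%, Section 5.1.2, Calibration), so skin or nerve events on that arm are a natural question for a validation study. The intravenous line is also placed on the EMG arm (5.1.1), and the cuff sits on that same arm (5.1.2). An arm event can therefore have competing device and drug explanations, which a drug-only field cannot separate.

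At stake is whether the trial's attribution data can say anything about the no-harm statement in Section 9. In the other direction, the threshold in 8.7 admits events that the investigator has graded as improbable.

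**Working it through.** No statistical figure is involved in the main point, so the check is to apply the rules as written.

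**1. Is there any route to a device attribution?** Take an injury for which the cuff is the evident cause.

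- Recorded? Yes. Section 8.1 counts events regardless of relatedness. If the event is serious, 8.5 and 8.6 send it to the sponsor regardless of causality.
- Graded? Under 8.4 the cuff is an evident cause other than the medication, so the grade is Not related.
- Attributed to the device? The only causality item in 8.2 concerns study medication, so there is nowhere to enter this.
- An adverse reaction under 8.7? No, because that definition needs a medicinal product.

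Capture works and attribution does not. The same holds for all 250 planned patients.

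**2. Does this follow for every arm event?** No. It follows when the cuff is the evident cause. An event of unclear origin could receive another grade, because the alternative explanations named in 8.4 are disease, other drugs or chemicals.

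**3. The Unlikely grade.** Section 8.4 places it under Related and defines it as making causality improbable. Section 8.7 requires a reasonable causal relationship and then sets the bar at this same grade. An event judged improbable is therefore an adverse reaction. If it is also serious and unexpected, it is a SUSAR on the 7- or 15-day reporting clock.

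**4. AE window against end of study (minor).** Inputs are 5 + 5 inclusions per week (11.4), a 7-day window (8.1, 8.5) and a total of 250. The window is assumed to start on the day of surgery, since the text describes no separate completion visit and the study outline figure is not available.

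- Both sites recruiting: (5 + 5) × 1 week = 10 patients with an open window at study end; 10/250 = 4%.
- One site recruiting at the end (assumption, prompted by the June 2019 amendment moving 50 patients to the LUMC): 5 × 1 = 5 patients; 5/250 = 2%.

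**The case against.** The strongest reply is that no harm is hidden. AEs are recorded whether or not they are thought related, with severity, other action taken, outcome and seriousness. SAEs reach the sponsor within one business day, and the data safety committee reviews CRF data regularly and after any SAE. This stands. A reader might infer that the trial would report no device harm whatever the cuff does, but the documents do not support that: a cuff injury would be visible in the record. Only its attribution to the device is lost.

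A reader might also infer that ordinary surgical complications will be counted as reactions to rocuronium and inflate a reaction count. That does not follow. Surgery is itself an evident other cause, so such events can be Not related under the same clause that catches the cuff. Section 7 plans no reaction count. It can also be said that 8.4 and 8.7 agree with each other and that a low bar errs towards over-reporting. Both points are fair, but they do not explain how an improbable cause can be a reasonable one.

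A third tempting reading is that follow-up of the last patients is cut short. Section 11.4 uses its definition for notifying the ethics committee and for the final report, and 8.2 already continues AE collection past completion. The mismatch is an inconsistency and does not show lost follow-up.

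Finally, cuff exposure could be put at 47 to 94 readings per patient (47 minutes to an EMG TOF ratio of 0.9 in Section 7.1, at 60- or 30-second intervals). That describes Group 1-type monitoring only. Group 2 is measured every 5 minutes between PTC 1 and 10. The figure should not be applied to everyone, and the point does not depend on it.

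**Conclusion.** The point holds as one about attribution. In all 250 patients, Section 8 offers no grade, CRF item or reaction definition through which an event can be tied to the TOF cuff or EMG stimulation, and an evident cuff injury is graded Not related. The attribution data therefore cannot test the harmlessness statement in Section 9. Separately, 8.4 and 8.7 together class an event judged improbable as having a reasonable causal relationship. The timing mismatch is minor, at about 5 to 10 patients (2% to 4%) under the assumptions shown.

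The conclusion rests on two assumptions. First, study medication is not defined on a page missing from the available text. Second, the term covers the anesthetic drugs that every patient receives. The second matters because 8.2 collects AEs from subjects who receive study medication, so the finding that capture works depends on that reading.

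Nothing here affects the agreement analysis, power or sample size. The changes are inexpensive and should be made.

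**What to change.** 1. Define study medication in Section 8.
2. Add to 8.2 a separate CRF item, and to 8.4 a separate causality assessment, for relationship to the study device or procedure (TOF cuff, EMG stimulation). Keep the drug item alongside it.
3. Carry device-related events into 8.7 next to the medicinal-product wording, which does not use the term study medication and so needs its own edit.
4. Reconcile the Unlikely grade in 8.4 with the threshold in 8.7, so that an event judged improbable is not classed as having a reasonable causal relationship.
5. As a minor item, give the AE window one anchor and one closing point in 8.1, 8.2 and 8.5, and reconcile it with the end-of-study definition in 11.4.

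The cost is one extra CRF field and some wording. If item 5 is settled by moving the end of study, it falls about 7 days later.
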